13.0 CRITERIA FOR REMOVAL FROM STUDY

Patients will be removed from the study when any of the criteria listed below applies. The reason for removal from the study and the date the patient was removed must be documented in the Clinical Research Database system. Patients who come off study before their first radiological assessment from baseline for reasons other than disease progression or treatment related toxicities may be replaced.

All patients who have received at least one dose of both study treatments will be assessable for safety of the combination therapy. Patients evaluable for efficacy analysis will include all patients who have received at least one cycle of treatment with both epacadostat and pembrolizumab and assessable for response. Patients who are missing an assessment of response post baseline will not be considered evaluable for response unless they missed

the assessment due to progression of disease or treatment related toxicities in which case they will be considered non-responders for that time point.

In the absence of treatment delays due to adverse events, treatment with epacadostat and/or pembrolizumab may continue until one of the following criteria applies:

- Intercurrent illness that prevents further administration of treatment
- Intolerance of study treatment
- Patient decides to withdraw from the study
- Physician decides to withdraw a patient from the study for a reason not listed here
- Pregnancy in patient
- The patient is lost to follow-up
- Inability of the patient to comply with the requirement of the protocol for treatment or evaluation.
- End of study, whichever occurs first.

Due to the mechanism of action, subjects may experience growth in existing tumors or the appearance of new tumors prior to maximal clinical benefit of epacadostat and pembrolizumab. The patient may be allowed to continue study treatment after initial RECIST 1.1 defined progression if they are assessed by the treating physician to be deriving clinical benefit and tolerating study treatment. The treating physician may consult with the overall study PI for help with assessing the patient. Such patients should discontinue study therapy upon further evidence of progression at the discretion of the treating investigator.

Safety follows up and End of Study visit

Upon permanent discontinuation from the study treatment for any reason, the following procedures will be performed approximately 30 (+7) days after the last dose of epacadostat or the last dose of pembrolizumab, whichever is later.

Full medical history, physical exam, assessment of performance status by KPS or ECOG status

Review of concomitant medications

Complete vital signs (pulse, blood pressure, temperature, respiratory rate, oxygen saturation) as well as weight and height. Height may be documented at any time prior to registration.

12-lead electrocardiogram (ECG)

Serum -HCG or urine pregnancy test for women with child-bearing potential. If the urine test is positive or cannot be confirmed as negative, a serum pregnancy test will be required.

Complete blood count with differential, including lymphocyte and eosinophil count.

Comprehensive metabolic panel (glucose, blood urea nitrogen, creatinine, sodium, potassium, chloride, bicarbonate, calcium, total protein, albumin, serum bilirubin, alkaline phosphatase, ASL, AST) phosphorus, magnesium

TSH, T4 free, T3

Amylase and lipase

An optional biopsy will be offered at progression of disease.

Patients whose treatment is interrupted or permanently discontinued due to an adverse event or clinically significant laboratory value must be followed until resolution or stabilization of the event.

Reporting of adverse events will occur for up to 90 days for serious adverse events (within 90 [+7] days after the last administration of epacadostat or pembrolizumab, whichever is later), Events of Clinical Interest (within 90 [+7] days after the last administration of epacadostat or pembrolizumab, whichever is later), and documentation of concomitant medications.

Long-Term Follow-up Procedures:

All subjects who permanently discontinue study drug for any reason other than withdrawal of full consent will be contacted by clinic visit or telephone to assess survival and initiation of additional sarcoma therapy. Contact for all subjects will be attempted every 12 weeks (±28 days) following the safety follow-up visit until death, subject withdraws full consent, or up to 12 months after the end of treatment.

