as long as patient is clinically benefitting, is tolerating the drug well and continues to meet all study treatment criteria.

The safety of the combination of epacadostat and pembrolizumab in patients with advanced sarcoma will be determined using CTCAE v4.03 criteria for toxicity assessment. Safety data will be collected for up to 90 days following the last dose of the study drugs. Therapy will be discontinued due to confirmed progression of disease or clinical progression, intercurrent illness that prevents further administration of treatment or intolerance of study treatment. Study personnel will attempt to collect survival status for all patients after the end-of-study visit every 3 months via telephone, email, or another method for up to 1 year.

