9.3 Duration of Therapy

Study treatment may continue until one of the following criteria applies:

Until a total of 35 cycles (approximately 2 years) of treatment has been administered as long as subjects are receiving benefit from treatment and have not had disease progression or met any criteria for study withdrawal outlined below

Clinical or radiographic disease progression as defined by RECIST 1.1. Patient may be allowed to continue treatment after progression if they are deriving clinical benefit (section 9.4).

Intercurrent illness that prevents further administration of treatment

Intolerance of study treatment

Patient decides to withdraw from the study

Physician decides to withdraw a patient from the study for a reason not listed here

Pregnancy in patient

The patient is lost to follow-up

Inability of the patient to comply with the requirement of the protocol for treatment or evaluation.

End of study, whichever occurs first.

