12.11 Overall Survival (OS)

OS is defined as the observed length of life from start of study treatment to death or the date of last contact.

12.12 Secondary Response Criteria - Immune-related Response Evaluation Criteria in Solid Tumors (irRECIST)

In 2013, Nishina et al. demonstrated that immune-related response criteria using unidimensional measurements were highly concordant with the bidimensional results of irRC, but with less measurement variability. ⁵⁵ Based on these findings and in order to utilize both the established criteria of irRC and RECIST 1.1, the two systems have been adapted, modified, and combined into the Immune-related Response Evaluation Criteria in Solid Tumors (irRECIST). The adapted irRECIST criteria are modifications to the irRC, incorporating the findings of Nishina et al. and the advantages of RECIST 1.1 while overcoming the shortcomings of each of the other guidelines.

irRECIST

Immune-related RECIST (irRECIST) guidelines according to Bohnsack et al. are presented below.

I. Baseline Assessments in irRECIST

In irRECIST, baseline assessment and measurement of measurable/non-measurable and target/non-target lesions and lymph nodes are in line with RECIST 1.1.

One new definition is added: If a subject has no measurable and no non-measurable disease at baseline the radiologist will assign 'No Disease' (irND) as the overall tumor assessment for any available follow-up time points unless new measurable lesions are identified and contribute to the total measured tumor burden (TMTB). irND is a valid assessment in studies with adjuvant setting where the protocol and study design allow the inclusion of subjects with no visible disease

Follow-up Assessments in irRECIST

A. Follow-up recording of target and new measurable lesions

The key difference in irRECIST is that the appearance of new lesions does not automatically indicate progression. Instead, all measured lesions (baseline-selected target lesions and new measurable lesions) are combined into the total measured tumor burden (TMTB) at follow up. Baseline-selected target lesions and new measurable lesions are

NOT assessed separately. Measurements of those lesions are combined into the TMTB, and one combined assessment provided.

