14.2 Secondary Endpoints

Secondary endpoints include:

1. Safety

Patients evaluable for safety analysis will include all patients who have received at least one dose of epacadsotat and pembrolizumab. Adverse events will be graded according to the NCI CTCAE v4.03, presented on an individual basis and summarized using descriptive statistics.

2. Survival

Progression free survival (PFS) rate at 24 weeks, median PFS, overall survival (OS) and progression-free survival intervals will be estimated using Kaplan-Meier methodology

3. Best Objective Response Rate by irRECIST

Best objective response rate (complete response + partial response) by 24 weeks by immune-related response criteria (irRECIST), of epacadostat in combination with pembrolizumab in patients with metastatic and/or locally advanced, sarcoma.

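### Survival follow-up ends about 12 months after treatment stops, so Kaplan-Meier OS beyond about month 12 is exposed to informative censoring, probably upward

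*Combined protocol and SAP*

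**What the plan says.** Section 13.0 (long-term follow-up) sets the schedule: "Contact for all subjects will be attempted every 12 weeks (±28 days) following the safety follow-up visit", continuing "until death, subject withdraws full consent, or up to 12 months after the end of treatment". Section 4.1 uses a different anchor: survival status is sought "after the end-of-study visit every 3 months via telephone, email, or another method for up to 1 year".

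Section 12.11 gives the endpoint: "OS is defined as the observed length of life from start of study treatment to death or the date of last contact". Section 14.2 gives the analysis: "overall survival (OS) and progression-free survival intervals will be estimated using Kaplan-Meier methodology".

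Section 9.3 lists what ends treatment: clinical or radiographic progression, intercurrent illness, intolerance, withdrawal, physician decision and others. The maximum is set by "Until a total of 35 cycles (approximately 2 years) of treatment has been administered". Section 9.4 allows treatment past RECIST progression for patients judged to be benefiting and tolerating it.

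No section sets a common survival cut-off, a time limit on OS reporting, or a sensitivity analysis for informative censoring.

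**The concern.** Kaplan-Meier is valid when a patient censored at time t has the same outlook as those still at risk at t. Here the planned censoring time is fixed by treatment duration. A patient who stops at the first scan is followed to about month 14, and one who completes treatment to about month 36. Between those times the risk set shifts towards patients who stayed on treatment longer. If they also live longer, the late curve describes them rather than the whole cohort.

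OS is a secondary objective (2.0), and a secondary hypothesis in 1.0 is that the combination improves it. With no control arm, any reading of OS rests on outside figures such as the protocol's own 10 to 18 months. The OS data also feed the biomarker survival analyses in 14.3.

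**Working it through.** **Plan's own figure.** The plan states no OS figure. Its one computable design figure, at least 6 responses in 30, reproduces (exact type I error 0.0732, power 0.9234, against 0.07 and 0.92 in 14.1) but does not bear on this point.

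**Inputs from the documents.** Follow-up ends 12 months after end of treatment (13.0). Treatment runs to at most 35 cycles of 21 days (9.3). Median survival is 10–18 months (1.0) or 10–15 months (3.0). There are 30 patients in one arm (14.1).

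**Assumptions, not in the documents.** Median treatment duration D (2, 4 or 6 months; 3 months to progression in the frailty model) and the strength of its link to survival.

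**Step 1: censoring times.** C = D + 12 months.
- Stop at week 8: 56 days ≈ 1.8 months, so C ≈ 13.8 months.
- Full course: 35 × 21 = 735 days ≈ 24.1 months, so C ≈ 36.1 months.
- Under 4.1 the year starts at a visit about 30 days after last dose: 30 + 365 = 395 days ≈ 13 months.

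**Step 2: 24-month OS, shared-frailty model.** OS = time to progression + post-progression survival. A log-normal frailty shared by both has SD 0, 0.5 or 1.0. Treatment ends at progression or 24 months.

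| True median OS (months) | Frailty SD | True (%) | Kaplan-Meier (%) | Difference (points) |
|---|---|---|---|---|
| 12 | 0 | 17.1 | 18.4 | +1.3 |
| 12 | 0.5 | 22.1 | 25.7 | +3.6 |
| 12 | 1.0 | 29.3 | 34.0 | +4.7 |
| 15 | 0 | 27.9 | 29.1 | +1.2 |
| 15 | 0.5 | 31.2 | 35.8 | +4.6 |
| 15 | 1.0 | 35.8 | 41.6 | +5.8 |
| 18 | 0 | 36.8 | 38.0 | +1.2 |
| 18 | 0.5 | 38.4 | 43.3 | +4.9 |
| 18 | 1.0 | 41.4 | 47.9 | +6.5 |

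SD 0 still gives a small bias because time on treatment is itself part of OS.

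**Step 3: other models** (Kaplan-Meier minus truth, percentage points).

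| Model | 18 months | 24 months |
|---|---|---|
| OS = D + independent exponential survival | +0.1 to +1.4 | +0.1 to +3.5 |
| Gaussian copula of D and OS, rho 0 | about 0 | about 0 |
| rho 0.3 | +1.3 to +1.5 | +3.0 to +3.8 |
| rho 0.6 | +2.2 to +2.8 | +5.5 to +7.4 |
| rho 0.8 | +2.4 to +3.6 | +7.2 to +10.4 |
| Separate shared-frailty model | +1.7 | +4.2 |
| Heterogeneous post-treatment survival unrelated to D | −0.1 to −1.5 | −0.9 to −4.5 |

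The smallest values in the first row come from the shortest treatment duration. Using 13 instead of 12 months (run in that first model) shrinks the bias but does not remove it: with true median 18 and D 6 months, +3.5 becomes +2.7 at 24 months.

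**Step 4: median OS.** A true 12 reads 12.0. A true 15 reads 15.1 to 15.6 in the frailty model and moves by at most about 0.1 in the first model of step 3. A true 18 reads 18.2, 19.1 and 21.1 in the frailty model (SD 0, 0.5, 1.0), 18.0 to 18.6 in the first model, and 19.0, 20.8 and 24.3 in the copula at rho 0.3, 0.6 and 0.8.

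**Step 5: month 12 itself.** With follow-up exactly to D + 12 months, every model gives zero bias at 12 months. The real schedule is coarser. Contacts fall about 30 + 84 = 114, 198, 282 and 366 days after last dose, so the fourth sits at the limit. A week-8 stopper last reached on day 282 is censored at 56 + 282 = 338 days, about month 11. If follow-up effectively ends at day 282, the frailty model gives about +0.4 to +1.1 points at 12 months.

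**Step 6: does a common cut-off cure it?** With n = 30, median OS 12.5 and D 4 months in the first model of step 3, the truth is 30.9% at 18 months and 17.4% at 24. The rule as written averages 31.7% and 19.4%; a common 36-month cut-off averages 30.7% and 17.3%.

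**The case against.** A reader might infer that the plan makes OS biased upward as a certainty. The documents do not support that. They give no relation between treatment duration and later survival, and the direction depends on it: independence gives no bias, and one plausible structure gives a downward one. Nor is the mechanism simply how long treatment worked. Treatment also ends for toxicity, withdrawal or physician decision, may continue past progression (9.4), is capped at 35 cycles, and may be resumed after two years (9.1). These loosen the link. They probably do not reverse it, since stopping for illness or intolerance and continuing only with clinical benefit both tie duration to prognosis.

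The practical case against is also fair. Section 14.2 names no 24-month OS rate. The median barely moves over most of the documents' range. About 1.5 to 10 of 30 patients remain at risk at 18 months and 0.2 to 6.5 at 24. In the frailty model the sampling SD of 24-month OS is 10 to 16 points, more than the bias. OS is descriptive, with no test or decision rule. All of this lowers the weight of the point. It does not remove a systematic error in a named secondary endpoint, and sparse late data are a further reason to limit what is reported.

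**Conclusion.** The concern holds as a risk of informative censoring after about month 12, with upward the probable direction. Under a positive link between duration and survival, the size is roughly 0 to 3 points at 18 months and 1 to 7 at 24, up to about 10 under strong dependence. It is smaller where treatment is short and later survival is unrelated to it. The median is little affected if truly 10 to 15 months. If near 18 it can be overstated by about 0 to 3 months, and by about 6 at the strongest dependence tried (24.3 against 18.0). These sizes rest on assumed treatment durations and dependence.

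A reader might also infer that 12-month OS is fully protected. That holds only if status is known through month 12 for everyone; last-contact censoring on a 12-weekly schedule can fall just short. The primary endpoint and 24-week PFS are unaffected, because both are read from tumour assessments well before month 12. This is worth correcting but does not threaten the trial's main conclusion.

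**What to change.** Preferred: in 13.0, ascertain vital status for every patient to one common limit, either a single data cut-off or a fixed time from first dose, using the planned telephone contact or a record check. Section 16.3 refers to the study as completed; if so, a retrospective record check still serves.

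Otherwise: state in 14.2 that OS is reported only to about 12 months from first dose, with numbers at risk. Add a final vital-status check at or after that time, so that 12-month status is complete apart from consent withdrawals.

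In either case give 4.1 and 13.0 the same anchor; at present they differ by about a month.

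Cost: a few extra calls or record checks for patients who stop early, or loss of a late OS curve that rests on few patients anyway.

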14.0 BIOSTATISTICS

14.1 Primary Endpoint

The primary objective is to evaluate the efficacy, as assessed by the best objective response rate (complete response + partial response) by 24 weeks by RECIST 1.1. The study will use a one stage design based on the exact binomial test. A 10% response rate will be considered not promising; a 30% response rate will be considered promising. There will be a maximum accrual of 30 patients to this study. It will be concluded that the true response rate is > 10% if there are 6 or more patients with an objective response among 30 patients. The design has a type I error rate of 0.07 and a type II error rate of 0.08. This design provides 92% probability of a positive result if the true response rate is at least 30%, and a 93% probability of a negative result if the true response rate is 10% or lower.

The patient population in this study represents patients with locally advanced/metastatic sarcoma that have received at least one line of previous therapy. The data supporting the 10% null rate comes from the SARC028 study that evaluated the efficacy of pembrolizumab monotherapy among patients with advanced/metastatic sarcoma which is discussed further below. In assessing the efficacy of a combination therapy incorporating pembrolizumab in this study population a response rate of> 10% would be preferred to determine the therapy as having a signal of efficacy.

Patients evaluable for efficacy analysis will include all patients who have received at least one cycle of treatment with epacadostat and pembrolizumab and are assessable for response. Patients who are missing an assessment of response post baseline will not be considered evaluable for response unless they missed the assessment due to progression of disease or treatment related toxicities in which case they will be considered non-responders for that time point. Patients who miss an assessment of response post baseline for any reason other than progression of disease and treatment related toxicity will be replaced.

Are knowledge regarding the efficacy of immunotherapy in sarcoma is evolving. As previously outlined, two studies evaluating the role of anti-PD1 monotherapy in patients with sarcoma were presented at the ASCO annual meeting in 2016. One study confirmed that no responses were seen among 12 patients with uterine LMS treated with nivolumab.²¹ The second study evaluated pembrolizumab in bone and soft tissue sarcomas (SARC028).²⁰ Signals of efficacy were observed in patients with UPS, liposarcoma (poorly differentiated/defferentiated) and chondrosarcoma. The objective response rates observed in this study was 19% for soft tissue sarcoma and was 5% for bone sarcoma. The objective response rates observed in this study for specific histologic subtypes were as follows: UPS -44%; liposarcoma -22%; synovial sarcoma 11%; leiomyosarcoma - 0%; chondrosarcoma - 17%; ewing's sarcoma - 0%; osteosarcoma - 5%. In relation to this trial design, patients with sarcoma subtypes where limited benefit from anti-PD1 monotherapy was observed in

previous studies may benefit from the combination immunotherapy approach offered in this study. Therefore, patients will be accrued based on histological sarcoma subtype into one of 4 cohorts. This will ensure that we enroll patients with an adequate spead of sarcoma histologies. Each cohort will enroll a prespecified number of patients with specific sarcoma histological subtypes. Due to the small sample size in each cohort, a sufficiently-powered efficacy analysis for each cohort is not possible however, the objective response rate for i) soft tissue sarcomas ii) bone sarcomas (if applicable depending on enrolment), and iii) within each cohort +/ each histological sarcoma subtype will be examined to look for a potential signal of efficacy.

We expect to accrue approximately 1-2 patients each month and hence expect to finish enrollment in 15-20 months.

The anticipated accrual rate for each cohort is as follows:

- A) Undifferentiated Pleomorphic Sarcoma (UPS)/ Liposarcoma (dedifferentiated or pleomorphic liposarcoma) one patient every month
- B) Leiomyosarcoma one patient every second month
- C) Vascular Sarcoma Subtypes (including angiosarcoma, Epithelioid Hemangioendothelioma (EHE),)- one patient every 3-4 months
- D) Other one patient every second month

14.2 Secondary Endpoints

Secondary endpoints include:

1. Safety

Patients evaluable for safety analysis will include all patients who have received at least one dose of epacadsotat and pembrolizumab. Adverse events will be graded according to the NCI CTCAE v4.03, presented on an individual basis and summarized using descriptive statistics.

2. Survival

Progression free survival (PFS) rate at 24 weeks, median PFS, overall survival (OS) and progression-free survival intervals will be estimated using Kaplan-Meier methodology

3. Best Objective Response Rate by irRECIST

Best objective response rate (complete response + partial response) by 24 weeks by immune-related response criteria (irRECIST), of epacadostat in combination with pembrolizumab in patients with metastatic and/or locally advanced, sarcoma.

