5.1.3 Administration of Epacadostat

Epacadostat be taken orally twice daily on a continuous dosing schedule at the recommended phase II dose for epacadostat when administered in combination with pembrolizumab. Epacadostat will be administered as a flat-fixed dose, and not by body weight or body surface area. Patients will be provided with a 3 week supply of epacadostat for self-administration at home until at least their next scheduled study visit. Patients will be instructed to return unused study drug to the site at each visit. A study medication diary will be completed by the patients for each dose of epacadostat.

Epacadostat will be taken twice daily orally without regard to food morning and evening, approximately 12 hours apart. There is no priority to the order of administration of epacadostat and pembrolizumab when given in combination; however, th dose of epacadostat should be taken as close to the regularly scheduled 12-hour dosing interval as possible. Patients will be instructed not to chew or crush tablets of study drug. If a patient vomits at any time after dosing, the dose of study drug should not be readministered. Doses of study drug omitted for AEs or any other reason should not be made up later in the day, or at the end of the dosing period. If a dose of epacadostat is missed, the subject should take it as soon as possible within 4 hours of the missed dose. If 4 hours passes, the subject should skip the missed dose and take the next dose as scheduled. All missed doses and schedule deviations should be recorded in the pill diary. Doses of epacadostat will be self-administered except on the days scheduled to be given at the time of a study visit.

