11.0 TOXICITIES/SIDE EFFECTS

Toxicity will be assessed using the NCI CTCAE (version 4.03). (http://ctep.cancer.gov/protocolDevelopment/electronic applications/ctc.htm).

Patients who have received at least one dose of the epacadostat and/or pembrolizumab are available for the safety assessment. Patients who discontinue the study before receiving their first dose of the study treatments will not be available for safety assessment and should be replaced.

Patients whose treatment is interrupted or permanently discontinued due to an adverse event or clinically significant laboratory value must be followed until resolution or stabilization of the event.

A dose delay >6 weeks from the date of the planned dose (i.e., approximately 9 weeks since the previous dose) may require the patient to be discontinued from the study, with exception of patients who undergo surgery. A dose delay >6 weeks from the date of the planned dose (i.e., approximately 9 weeks since the previous dose) due to the occurrence of an adverse event that is considered related to epacadostat and/or pembrolizumab, the subject should be taken off study treatment.

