r dosing prophylactic medications indicated for< = 24 hrs NSAIDS Acetaminophen Narcotics Increase monitoring of vital signs as medically indicated until the subject is deemed medically stable in the opinion of the investigator. If symptoms resolve within one hour of stopping drug infusion, the infusion may be restarted at 50% of the original infusion rate (e.g., from 100 mUhr to 50 ml/hr). Otherwise dosing will be held until symptoms resolve and the subject should be premedicated for the next scheduled dose. Subjects who develop Grade 2 toxicity despite adequate premedication should be permanently discontinued from further trial treatment administration. Grade 3: Prolonged (i.e., not rapidly responsive to symptomatic medication and/or brief interruption of infusion); recurrence of symptoms following initial improvement; hospitalization indicated for other clinical sequelae (e.g., renal impairment, pulmonary infiltrates) Grade 4: Life-threatening; pressor or ventilatory support indicated Increase monitoring of vital signs as medically indicated until the subject is deemed medically stable in the opinion of the investigator. Hospitalization may be indicated. Subject is permanently discontinued from further trial treatment administration. Appropriate resuscitation equipment should be available in the room and a physician readily available during the period	NCI CTCAE Grade	Treatment	Premedication at subsequent	

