11.6 AE and SAE reporting

11.6.1 Time Period and Frequency of Detecting AEs and SAEs

The investigator or site staff is responsible for detecting, documenting and reporting events that meet the definition of an AE or SAE. See section below for the timeline for reporting SAEs.

AEs and SAEs will be collected from the time the first dose of study treatment is administered until 90 days following discontinuation of study treatment regardless of initiation of a new cancer therapy or transfer to hospice.

After discontinuation of study treatment, the investigator will monitor all AEs/SAEs that are ongoing until resolution or stabilization of the event or until the subject is lost to follow-up. At any time after treatment discontinuation the investigator may report any adverse event that they believe possibly related to study treatment.

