12.2 Definitions

Evaluable for toxicity - Patients evaluable for safety analysis will include all patients who have received at least one dose of epacadsotat and pembrolizumab. Patients will be evaluable for toxicity from the time of their first treatment with epacadostat and pembrolizumab.

Evaluable for efficacy - Only those patients who have a measurable disease based on RECIST 1.1 criteria will be eligible for this study, as highlighted in Section 6.0. These patients will have their response classified according to the definitions stated below.

Only those patients who have measurable disease present at baseline, have received at least one cycle of the combination therapy, and have had their disease re-evaluated will be considered evaluable for response. (Note: Patients who exhibit objective disease progression prior to the end of cycle 1 will also be considered evaluable and determined to

Memorial Sloan Kettering Cancer Center IRB Number: 17-508 A(8)

Approval date: 07-May-2024

be non-responders. Note: one cycle of therapy consists of 21 days where the study therapy (epacadostat and pembrolizumab) is administered at the start of the cycle on day 1)

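### The safety analysis set is defined differently in Section 11.0 and in Sections 12.2, 13.0 and 14.2, and nothing says which definition governs

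*Combined protocol and SAP*

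**What the plan says.** Four sections of the combined protocol and SAP say who counts for safety.

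- **Section 11.0** takes a dose of either drug as enough: "Patients who have received at least one dose of the epacadostat and/or pembrolizumab are available for the safety assessment". The only patients it removes are those who stop before a first dose, who "will not be available for safety assessment and should be replaced".
- **Section 12.2** joins the two drugs with a plain conjunction and starts the clock the same way: "Patients will be evaluable for toxicity from the time of their first treatment with epacadostat and pembrolizumab".
- **Section 13.0** is explicit: "All patients who have received at least one dose of both study treatments will be assessable for safety of the combination therapy".
- **Section 14.2**, the statistical section, repeats the Section 12.2 rule: "Patients evaluable for safety analysis will include all patients who have received at least one dose of epacadsotat and pembrolizumab".

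Three other provisions bear on the point. Section 5.1.3 leaves the order of the drugs open: "There is no priority to the order of administration of epacadostat and pembrolizumab when given in combination". Table 17 in Section 11.5 says of a grade 3 or 4 infusion reaction: "Subject is permanently discontinued from further trial treatment administration". Section 11.6.1 starts event collection independently of any analysis set: "AEs and SAEs will be collected from the time the first dose of study treatment is administered".

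**The concern.** Safety is the first secondary objective in Section 2.0, and Section 14.2 plans only individual listings and descriptive summaries for it. The choice of analysis set therefore determines which rates are reported. An analyst working from Section 14.2 and one working from Section 11.0 could report different denominators.

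The difference matters most when a patient misses the second drug because of a reaction to the first. The narrower rule then removes a treated patient because of toxicity, which is the outcome being measured. With about 30 patients, each one is worth 3.3 percentage points.

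**Working it through.** **1. The plan's own figure.** The documents give no figure for the safety set. The only design figure is the primary rule in Section 14.1: 6 or more responders among 30, null rate 10%, promising rate 30%. With X binomial, P(X ≥ 6 | 30, 0.10) = 0.0732 and P(X ≥ 6 | 30, 0.30) = 0.9234. The type II error is 1 − 0.9234 = 0.0766. These match the stated 0.07, 92% and 0.08. The calculation does not use the safety set, so this point leaves it unchanged.

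**2. Can a patient fall between the definitions?**

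- Both drugs start on day 1 (Sections 4.1 and 4.2), in either order (Section 5.1.3).
- Suppose pembrolizumab is given first, a grade 3-4 infusion reaction occurs, and trial treatment ends under Table 17 before any epacadostat is taken.
- Under Section 11.0 the patient is in the safety set, provided a partly given infusion counts as a dose. The documents do not say whether it does.
- Under Section 13.0, and on the plain reading of Sections 12.2 and 14.2, the patient is not in the set.
- The mirror case is a patient who takes epacadostat first and stops before the infusion.

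**3. Size when toxicity causes the exclusion.** The documents give no frequency for single-drug exposure, so the count k is an assumption. Take 30 treated patients with no replacement. Let k of them receive one drug only, each stopping because of the event, and let nobody else have that event. The either-drug rate is k/30 and the both-drugs rate is 0/(30 − k). Intervals are exact (Clopper-Pearson) 95%. For zero events the upper limit is 1 − 0.025^(1/n); for n = 29 this is 11.9%.

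| k (assumed) | Either drug (11.0) | Both drugs (14.2, plain reading) |
|---|---|---|
| 0 | 0/30 = 0% (0-11.6%) | 0/30 = 0% (0-11.6%) |
| 1 | 1/30 = 3.3% (0.1-17.2%) | 0/29 = 0% (0-11.9%) |
| 2 | 2/30 = 6.7% (0.8-22.1%) | 0/28 = 0% (0-12.3%) |

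If 5 patients who received both drugs also have the event and k = 1, the rates are 6/30 = 20.0% and 5/29 = 17.2%.

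**4. Size when the exclusion has another cause.** Suppose one patient leaves after one drug without the event, and 5 others have it. The either-drug rate is 5/30 = 16.7% and the both-drugs rate is 5/29 = 17.2%. The shift is small and upward.

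**5. Chance that the case arises.** For an assumed per-patient probability p, the chance of at least one such patient in 30 is 1 − (1 − p)^30. This gives 26% at p = 1%, 45% at 2% and 79% at 5%. None of these values of p comes from the documents.

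**The case against.** The strongest case against is that this is a wording mismatch with little practical effect. Sections 12.2 and 14.2 say who will be included and do not say that only those patients count. Section 12.2 does use restrictive wording for the response set, so the authors had it available. Section 13.0 speaks of the safety of the combination, which may describe a narrower purpose. Events are collected from the first dose whatever the set is called. The gap on day 1 is short, and the illustrative intervals overlap heavily. Section 16.3 also describes the study as completed.

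Much of this stands. It limits the effect to a summary denominator and the rates built on it, and it makes an express exclusion an inference. It does not remove the inconsistency. Section 11.0 shows that the authors wrote an either-drug rule when they meant one, Section 13.0 supports reading the conjunction in Sections 12.2 and 14.2 as requiring both drugs, and no separate combination set is defined.

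A reader might infer three stronger things that the documents do not support:

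- **That the rates can only be biased downward.** This holds for exclusions caused by toxicity. Patients who leave after one drug for unrelated reasons can move rates the other way.
- **That the patient disappears from efficacy as well.** Sections 13.0 and 14.1 require one cycle of treatment, but they also count an assessment missed through treatment-related toxicity as non-response. Which provision applies is unclear. Such a patient might even count against efficacy while missing from safety.
- **That the event itself is lost.** Section 11.6.1 keeps it in the collected data.

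**Conclusion.** The inconsistency is real, and the protocol's own dosing-order and discontinuation provisions make the gap reachable. On the plain reading of Section 14.2, a patient stopped by a reaction to the first drug is left out of the safety summary rates. Each such patient lowers an event rate by roughly 3 percentage points, and an event confined to such patients would be summarised as 0%.

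The size rests on assumed counts of 0 to 2 in 30, no replacement, and the both-drugs reading of Sections 12.2 and 14.2. If every treated patient received both drugs, all the definitions give the same set. Few patients are likely to be affected, no test or threshold is attached to the safety summary in Section 14.2, and the primary endpoint is untouched. Severity is minor.

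**What to change.** In Sections 12.2, 13.0 and 14.2, define the safety set as all patients who received at least one dose, in any amount, of epacadostat or pembrolizumab, evaluable from the first dose of either drug. This follows Section 11.0, where the any-amount wording should also be added so that an interrupted infusion counts. Use this denominator in the study report and state it there. A subset who received both drugs may be shown as a labelled supplementary table.

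The cost is one sentence in each section. No new data are needed, because events are already collected from the first dose. Reported toxicity may be slightly higher if any patient stopped after one drug because of a reaction.
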